7.1. Subgroup analyses

No subgroup analyses are planned.

7.2. Other aspects

a. Multiplicity

A p-value of < 0.017 will be considered as statistically significant to account for the fact that we make three comparisons. Interim analyses will be performed, but these analyses will not influence the continuation of the study.

b. Missing data

Data will be used until time point at which participant is last seen. If there are intermediate missing results, these will be considered to be negative for leprosy.

8. Analysis of secondary efficacy objectives

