2.1. Study design

The PEOPLE study is a cluster randomized trial. There will be four door-to-door surveys of which the first one will allow us to calculate a baseline leprosy prevalence

per island. On the Comoros villages have been randomized after having been grouped by island into 'Blocks' of four in decreasing order of incidence over the period 2013-2017. Within each block villages were randomly and mutually exclusively allocated to the four study arms. For the study district in Madagascar reliable incidence estimates were not available. For that reason randomization for Madagascar is foreseen only for the end of the first study year, once the first screening round has been completed.

There will be four study arms to which villages on Madagascar and the Comoros islands Anjouan and Mohéli will be randomly allocated. These villages have been preselected based on reported leprosy incidence over the period 2013-2017. In all four study arms, annual door-to-door surveys will be conducted covering entire villages. All permanent residents will be invited for screening for leprosy. Leprosy patients (further referred to as 'index patients') detected will be offered free treatment according to the international and country guidelines. Depending on the study arm, contacts of leprosy patients will be offered PEP. In arm 1 no PEP will be provided, which is the current routine care on Madagascar and the Comoros. In arms 2, 3 and 4 a single dose of 20 mg per kg bodyweight of Rifampicin (hereafter called 'SDDR-PEP') will be offered to all eligible participants who have not received Rifampicin in the preceding 2-year period. In arm 2 only household contacts of an index patient will be provided with SDDR-PEP, which target group is considered the standard approach when PEP is provided for leprosy. In arms 3 and 4 SDDR-PEP will also be provided to neighbourhood contacts living within a radius of 100 meter of an index patient. In arm 3 all such contacts (including household contacts) will be provided SDDR-PEP, in arm 4 SDDR-PEP will be provided to all household contacts and to all those within the 100-meter perimeter testing positive to a serological screening test. If in arms 3 or 4 more than 50% (arm 3) or 75% (arm 4) of the population live within 100 meters of an index case, the entire village will in principle be eligible for PEP.

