We will fit a random effects Poisson model with incident case (0/1) as dependent variable, study arm as explanatory variable, using the non-intervention group (arm 1) as baseline level, log(time at risk) as offset, and with 'island', 'block' (as described above, eight on Anjouan, four on Mohéli, four to six on Madagascar) and 'village' as nested random effects. As study outcome we will report incidence rate ratios between arm 1 and each of the other arms with 95% confidence interval, considering a p-value of < 0.017 as statistically significant to account for the fact that we make three comparisons.

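### The fixed 0.017 cut-off for all three primary comparisons gives away power that Holm's step-down would keep at the same family-wise error

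*SAP*

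**What the plan says.** SAP Section 7 fits a random effects Poisson model "using the non-intervention group (arm 1) as baseline level". The results to be given are "incidence rate ratios between arm 1 and each of the other arms with 95% confidence interval". The same sentence sets the threshold for significance at 0.017 for every comparison. Section 7.2, under Multiplicity, repeats the cut-off: "A p-value of < 0.017 will be considered as statistically significant to account for the fact that we make three comparisons". Neither section gives a step-down rule, an ordering of the hypotheses or a gatekeeping scheme, so each of the three p-values is compared with 0.017 whatever the other two show. The correction is not named and the overall 5% level is not printed; both are inferred from the value. On the interim looks, Section 7.2 adds: "Interim analyses will be performed, but these analyses will not influence the continuation of the study".

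**The concern.** Bonferroni protects against three false null hypotheses being wrongly claimed as if all three nulls were still in play. Once one has been rejected, either that rejection is correct and at most two true nulls remain, or the family-wise error has already been made. Holding the remaining tests to 0.05/3 therefore buys no protection at the 5% level. Holm uses this fact and needs no further assumption about how the tests are related.

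This matters here for three reasons.

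- The primary objective (Section 2.2) concerns three approaches to prophylaxis. One positive arm answers only part of it, and Holm's gain falls on the second and third rejections.
- All three intervention arms offer the same single-dose regimen, and all cover household contacts (Section 2.1). If prophylaxis works, benefit in more than one arm is plausible, and that is where the fixed cut-off loses most.
- Sections 1 and 6 say that the interim looks are there to see whether the assumed incidence was realistic. A trial that may have fewer events than planned has little reason to discard power that costs nothing in type I error.

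**Working it through.** **Reproducing the plan's figure.** Three comparisons at an overall two-sided 5% (inferred):

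- Bonferroni: 0.05/3 = 0.01667, which rounds to 0.017.
- Šidák: 1 − 0.95^(1/3) = 0.01695, which also rounds to 0.017.
- Union bound of the printed rule: 3 × 0.017 = 0.051.

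**The two rules.** Order the p-values p(1) ≤ p(2) ≤ p(3).

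- Bonferroni: reject every hypothesis with p ≤ 0.05/3 = 0.0167.
- Holm: reject the first if p(1) ≤ 0.05/3 = 0.0167; then the second if p(2) ≤ 0.05/2 = 0.025; then the third if p(3) ≤ 0.05. Stop at the first failure.

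Each Holm threshold is at least 0.05/3, so any set of p-values rejected at 0.05/3 is also rejected by Holm. That holds for any effect size and any correlation.

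**Inputs for the size of the gain.**

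- From the SAP: three comparisons with a shared arm 1, and equal allocation by village on the Comoros (Section 2.1: "Within each block villages were randomly and mutually exclusively allocated to the four study arms").
- Assumed: correlation 0.5 between the test statistics, which follows from a shared control if the arms carry equal information.
- Assumed: power per comparison at 0.05/3 of 80%, with 60% as a second case. The SAP prints no power or effect size.
- No alpha is charged to the interim looks, in line with Section 7.2.

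**Calculation.** Three two-sided z-tests were simulated. The critical value at 0.05/3 is 2.394. The mean giving 80% power is 3.236, and 2.647 gives 60%. Two million draws per scenario, correlation 0.5:

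| Scenario | Per effective arm, 0.05/3 → Holm | All three arms, 0.05/3 → Holm |
|---|---|---|
| Three effective arms, 80% | 80.0% → 86.5% | 61.2% → 76.7% |
| Three effective arms, 60% | 60.0% → 67.8% | 35.0% → 52.1% |
| Two effective arms, 80% | 80.0% → 82.8% | not applicable |
| One effective arm, 80% | 80.0% → 80.1% | not applicable |

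If the starting power is set at 0.017 instead of 0.05/3, the first row becomes 86.2% per arm and 76.4% for all three.

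If the three effects stand in the ratio 1:2:3, with 80% power for the largest, per-arm power goes from 9.4%, 40.6% and 80.0% to 16.7%, 46.7% and 80.9%.

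The probability of at least one significant arm is identical under both rules (95.0% in the first row), because the first step is the same.

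**Family-wise error under Holm.**

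- All three null: 4.4%, the same as Bonferroni at 0.05/3.
- One effective arm and two null: 4.2%.
- Two effective arms and one null: 3.9%, against 1.7% under Bonferroni.

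All are below 5%.

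**The case against.** The case for leaving the rule alone is that nothing in it is wrong. The cut-off is pre-specified, agrees between the two sections and controls the family-wise error. That stands: this is a point about efficiency.

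Several limits on the gain also stand.

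- The largest figures need three equally effective arms, whereas the arms treat different groups of contacts. With graded effects the gain is smaller.
- The chance of at least one positive arm is unchanged.
- Holm obtains its power by using error that Bonferroni leaves unspent. With two effective arms, the false-positive rate for a null third arm more than doubles, from 1.7% to 3.9%. It remains within the 5% that the plan is taken to accept.
- The printed 0.017 lies slightly above 0.05/3, so a smallest p-value between 0.01667 and 0.017 would pass the SAP's rule and fail Holm's first step. Holm's dominance is over 0.05/3, not over the rounded figure. In practice this is trivial.
- The power levels and the correlation are assumed. The protocol may hold a sample-size basis for 0.017, so it cannot be said from the SAP alone that power is short.

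The strongest argument for Bonferroni is that each test has a simple matching interval, at 98.3%. Under Holm, one arm's result depends on the others, and the interval can include 1 for a rejected hypothesis. But the SAP does not use this advantage. It reports "each of the other arms with 95% confidence interval" beside a 0.017 threshold, so an interval can exclude 1 while a p-value between 0.017 and 0.05 is called non-significant.

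**Conclusion.** The concern holds as an optional improvement and not as an error. Holm at family-wise 5% controls the same error as 0.05/3 under any dependence and never rejects less, so the direction of the gain needs no assumption about effects. Its size does. From 80% power per comparison with a shared control, the gain is about 6 percentage points per arm and 16 points for all three if every arm works equally well, about 3 points per arm if two work, and practically nothing if only one does. There is no gain in the chance of finding at least one effective arm.

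**What to change.** In Sections 7 and 7.2, replace the fixed 0.017 rule with Holm's step-down procedure for the three comparisons with arm 1 at a two-sided family-wise level of 5%. State the thresholds as 0.05/3, 0.05/2 and 0.05, which also removes the rounding. Report Holm-adjusted p-values beside the rate ratios.

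Report 98.3% intervals (1 − 0.05/3) as conservative simultaneous intervals. Any that excludes 1 is also significant under Holm. Say in the text that Holm may reject where such an interval just includes 1. If the 95% intervals are kept as well, label them as unadjusted.

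The cost is a matching edit in two sections and small changes to the results tables, which carry over to the interim reports because those follow the final analysis. No data collection or model changes. The edit should be fixed before any comparative result is seen, hence before the first interim analysis. After that point, Section 1 requires a major change of method to be described and justified in the statistical analysis report.

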5.2. Efficacy study endpoints

Primary endpoint

The primary efficacy objective is to compare leprosy incidence rate. The health worker will perform a physical examination to look for signs of leprosy. Note that for this study, the diagnosis of leprosy will be made based on the so-called cardinal signs, i.e. a patch with loss of sensation, enlarged peripheral nerves and/or a slit skin smear positive for

acid fact bacilli. Results of qPCR and anti-PGLI testing will be not be used as diagnostic criteria.

Secondary endpoints

Genotyping will be done by a novel sequencing technique called the Deeplex® MycLep assay.

Rifampicin resistance will be tested with molecular markers.

6. Interim analysis

Two interim analyses will be conducted upon completing the second and third door-to-door surveys in which leprosy incidence rates to date in study arms 2, 3 and 4 will be compared to the leprosy incidence rate in arm 1, just as in the final analysis. These interim analyses will allow us to assess whether the a priori assumptions on annual incidence made have been realistic or whether an extended study duration should be considered.

The analysis performed will be similar to the analysis of the main efficacy outcome (Section 7) but restricted to data up to the second resp. third survey. Hence the interim analysis after completing the second survey will only include data from the Comoros.

7. Analysis of main efficacy outcomes: incidence rate of leprosy

Each diagnosis of leprosy made after the survey in which the participant was enrolled will be counted as an incident case. Note that not only diagnoses made at the annual surveys but also diagnoses made in between the surveys will be counted. For each individual we will calculate the exact time at risk. For individuals residing in intervention villages (arms 2, 3 and 4) we will use the number of days from the median date of the first SDDR-PEP administration in the village until end of follow-up or until diagnosis of leprosy.

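### Time after the last attended survey counts only if it ends in leprosy: absolute incidence is inflated, and the rate ratio is biased if non-return or between-survey detection differs by arm

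*SAP*

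**What the plan says.** Section 7 of the SAP defines the events: "Each diagnosis of leprosy made after the survey in which the participant was enrolled will be counted as an incident case". It adds: "Note that not only diagnoses made at the annual surveys but also diagnoses made in between the surveys will be counted". For arms 2 to 4, time at risk runs from the village's median date of first SDDR-PEP administration "until end of follow-up or until diagnosis of leprosy". It enters the random effects Poisson model through "log(time at risk) as offset".

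Section 7.2 b gives the missing-data rule: "Data will be used until time point at which participant is last seen". For gaps in attendance it says: "If there are intermediate missing results, these will be considered to be negative for leprosy".

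Neither *last seen* nor *end of follow-up* is defined in the SAP. No sentence says whether a diagnosis made after a person's last attended survey is left out, and none extends time at risk for an undiagnosed person who stops attending.

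**The concern.** Take two people who attend the second survey and miss the third and fourth. One stays free of leprosy and was last seen at the second survey, so follow-up ends there. The other is diagnosed at a clinic six months later. Section 7 counts that event and runs time to the diagnosis. Six months of comparable follow-up exists for both, but only the person who became ill contributes it.

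The extreme case is a person never seen again after enrolment. Without a diagnosis, time at risk is about zero. In arms 2 to 4 it can be negative if the person was last seen before the village's median PEP date. The logarithm is then undefined and the person drops out of the model, although Section 5.1.1 says all participants are analysed. The same person, if diagnosed between surveys, stays in as an event provided the time is positive.

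The absolute rates matter in their own right. The interim analyses in Section 6 are meant to show whether the assumed annual incidence was realistic and whether a longer study should be considered. Absolute rates are also a natural input to the cost per case averted in Section 8.1. The incidence rate ratio, which is the reported outcome, is at stake only under a further condition, worked out below.

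**Working it through.** The SAP states no loss to follow-up, rate or power figure that bears on this point, so there is no plan figure to reproduce. Two quantities have to be assumed:

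- *L*: the share of all person-time that falls after a person was last seen.
- *p*: the share of the disease arising in that time that is diagnosed between surveys and therefore counted.

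**Inflation of the absolute rate.** Let the true rate be λ and total person-time T. Leprosy is rare, so the small extra time of the cases is ignored. Counted events are λT(1−L) + pλTL, and counted time is T(1−L). The ratio of the planned rate to the true rate is

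1 + p·L/(1−L).

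The share of counted events that comes from non-returners is 1 − 1/factor.

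| L | p | Factor | Share of events |
|---|---|---|---|
| 20% | 0.25 | 1 + 0.25 × 0.2/0.8 = 1.06 | 6% |
| 20% | 0.50 | 1 + 0.50 × 0.2/0.8 = 1.13 | 11% |
| 30% | 0.25 | 1 + 0.25 × 0.3/0.7 = 1.11 | 10% |
| 30% | 0.50 | 1 + 0.50 × 0.3/0.7 = 1.21 | 18% |

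With p = 0 there is no inflation. Intermediate missed surveys play no part, because they are set to negative and their time is kept.

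**Check with another parameterisation.** Assume three years of follow-up and permanent non-return of 10% at each survey. Time seen is then 2.439 years per person and time absent 0.561 years. The factor is 1 + 0.25 × 0.561/2.439 = 1.06, or 1.12 (1.115 before rounding) with 0.50. Simulations of 4 million people per scenario, at true rates of 1 and 2 per 1,000 person-years, gave 1.06 to 1.07 and 1.10 to 1.12.

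**Rate ratio when PEP has no effect.**

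- Equal L and p in both arms: the factors cancel and the ratio is 1.00.
- L = 20% in a PEP arm, 30% in arm 1: 1.0625/1.1071 = 0.96 (p = 0.25); 1.125/1.2143 = 0.93 (p = 0.50).
- L = 30% in a PEP arm, 20% in arm 1: 1.1071/1.0625 = 1.04; 1.2143/1.125 = 1.08.
- Equal L = 20%, with p = 0.25 in a PEP arm and 0.50 in arm 1: 1.0625/1.125 = 0.94; reversed, 1.06.

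**Behaviour of the two symmetric rules.** Closing everyone at the last attended survey and leaving out later diagnoses gave 0.99 to 1.01 of the true rate in every simulated scenario, with non-return simulated as unrelated to leprosy. Counting all diagnoses and running non-case time to closure gives 1 − L(1−p) of the true rate. At L = 20% that is 0.85 or 0.90; at L = 30%, 0.78 or 0.85 (p = 0.25 or 0.50). This second rule errs downward. With 20% against 30% as above, its null ratio is 0.85/0.775 = 1.10 or 0.90/0.85 = 1.06, the opposite direction from the planned rule.

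**The case against.** The strongest reply is that the asymmetry depends on how the text is read. Section 7.2 b is not limited to people without a diagnosis. If *last seen* means the last attended survey for everyone, a later clinic diagnosis is also cut off, and the protocol may define the term. But Section 7 counts each post-enrolment diagnosis without condition, and a clinic diagnosis is itself a sighting. The natural combined reading keeps the case and drops the healthy person's time. If the stricter reading is intended, it contradicts Section 7. Either way the two sections must be reconciled.

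The second reply is about materiality, and much of it stands. A reader might infer that the primary rate ratio is biased in favour of PEP, because villagers knew their arm and only arms 2 to 4 are offered a drug. The SAP does not support that. Section 4.1 connects knowledge of the arm with enrolment, not with later attendance, and the document has no data on non-return or between-survey detection by arm. The direction is also open, since more non-return in a PEP arm would hide a benefit.

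The assumed values are demanding too. With three yearly follow-up surveys and constant permanent non-return, L = 20% and 30% mean that about 29% and 42% of participants are gone by the last survey. If most non-returners have left the area, p may be near zero. At p = 0.1 and 20% against 30%, the null ratio is 1.025/1.043 = 0.98.

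Finally, closing at the last attended survey has a weakness of its own: diagnosis may change whether someone is present at the next survey, and that would bring outcome-dependent inclusion back.

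**Conclusion.** The point holds for absolute incidence. As written, Sections 7 and 7.2 b make follow-up after the last attended survey depend on the outcome, and rates are inflated whenever non-returners are diagnosed between surveys: by 6% to 21% for L of 20% to 30% and p of 0.25 to 0.50. For the incidence rate ratio the bias is conditional. It is nil if non-return and between-survey detection are equal across arms, and of either sign if they differ: 0.96 to 0.93, or 1.04 to 1.08 with the arms reversed, for 20% against 30%. These sizes rest entirely on assumed L and p. The trial's own attendance and diagnosis records would show which values apply.

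**What to change.** Define *last seen* and *end of follow-up* once, in Sections 7 and 7.2 b, and apply the same closing rule to cases and non-cases. Run the analysis both ways, with one named as primary in advance and the other as sensitivity analysis:

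- (a) close everyone at the last attended survey and leave out diagnoses made after it;
- (b) count all diagnoses and run all non-case time to the village's last survey, or to known departure or death.

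Report non-return and between-survey diagnoses by arm. Section 4.1 already plans attendance counts and losses to follow-up, but asks expressly for a breakdown by arm only for non-enrolment. State also how people with zero or negative time at risk are handled.

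In writing, the cost is a few sentences. In analysis, (a) removes the passively found cases in non-returners, about 6% to 18% of events under the assumed values, which is not trivial for a rare outcome. Rule (b) keeps them but understates rates if cases in non-returners go undetected. Because the two rules err differently, agreement between them would be reassuring, and a gap would show how much the result depends on non-return.

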8.1. To assess cost and feasibility of SDDR-PEP under program conditions

Costs will be calculated per person screened, per person treated with SDDR-PEP and per leprosy case averted.

8.2. To identify patterns of clustering in transmission of leprosy, allowing better targeting of control measures

Results of DNA finger printing will be used to assess the degree of clustering at household and at village level. We will calculate proportions of patients belonging to a same cluster by household and by village. The space-time K-function will be used to assess clustering in time and space, to be triangulated with results of DNA finger printing. For this purpose, we will use results of all leprosy patients identified, including those found at baseline.

To establish the transmission networks in the Comoros islands and in the study area in Madagascar, we will overlay the molecular network with the spatial- and social networks. This will determine whether the 100m high risk zones around each index patient, applied in this study, capture most transmission events, or whether additional risk factors, beyond spatial, need to be taken into account in future PEP administration efforts in the study areas and elsewhere. Phylogenetic clustering of the *M. leprae* isolates allows us to identify risk factors for leprosy due to recent transmission. The findings of the spatial and social network analysis can be mapped onto a phylogenetic tree and molecular clusters based on the VNTRs, which can reveal risk factors for transmission of leprosy.

Mixed effects Poisson model (same model as for the main analysis) with study arm (only when comparing 2019 to 2020 data) and distance to nearest index case as fixed covariates will be used to test for an association between distance to index case and leprosy incidence rate. We will compare six distance categories: same household, neighbors at < 25 meters and neighborhood contacts at 25-<50 meters, at 50 - < 75 meters, at 75 - < 100 meters and at 100 meters or beyond. Two models will be fitted. The first model will use leprosy diagnosis at the time of the survey in 2019 (either a new diagnosis or a patient still on treatment) as outcome and distance to nearest index case from 2019 as independent variable, the second model will use incident leprosy cases in 2020 as outcome and distance to nearest index case from 2019 as independent variable. In addition we will use Kulldorff's spatial scan statistic to fit a purely spatial Poisson model to identify clusters of high leprosy prevalence.

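### Section 8.2 pools patients of all arms and surveys to judge household and 100 m clustering, although PEP in arms 2-4 selectively removes later cases close to index patients

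*SAP*

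**What the plan says.** SAP section 8.2 has three parts that bear on this point.

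- **Fingerprinting and K-function.** The summary is "We will calculate proportions of patients belonging to a same cluster by household and by village". The space-time K-function is set beside it. For both, "we will use results of all leprosy patients identified, including those found at baseline". There is no split by arm, by survey or by receipt of PEP.
- **Network overlay.** Molecular, spatial and social networks are laid over one another. The stated aim is: "This will determine whether the 100m high risk zones around each index patient, applied in this study, capture most transmission events". No population is named. The result is meant to inform future PEP in the study areas and elsewhere.
- **Distance regression.** One model relates 2019 diagnoses to distance from 2019 index cases. A second relates incident 2020 cases to the same distances. Study arm is a covariate only in the second, as a fixed effect without an interaction with distance.

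Section 2.1 defines who gets PEP:

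- Arm 1: "In arm 1 no PEP will be provided".
- Arm 2: "In arm 2 only household contacts of an index patient will be provided with SDDR-PEP".
- Arms 3 and 4: "In arms 3 and 4 SDDR-PEP will also be provided to neighbourhood contacts living within a radius of 100 meter of an index patient". Neighbours in arm 4 must also test positive serologically.
- If more than 50% (arm 3) or 75% (arm 4) of a village lives within 100 m of an index case, the whole village becomes eligible in principle.

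Section 5.1 adds that first-survey data are also used for secondary objectives 2 and 3.

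**The concern.** The people who receive PEP are those whose disease would count as household transmission or as transmission inside the zone. A prevented case is never typed or mapped. A case far from any index patient is untouched by PEP unless the whole village was treated. Among later patients in arms 2, 3 and 4, the near share therefore falls as PEP works better.

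A pooled share mixes the natural pattern of transmission with the effect of the trial's own intervention. The objective is to target control measures better, and the question put to the data is whether the 100 m zone is wide enough. A good result for PEP inside the zone would count against the zone.

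**Working it through.** The SAP states no figure on this point, so there is nothing to reproduce. What follows is an illustration on assumed values.

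**Assumptions (none is in the SAP).** Without PEP, later cases are 20% household, 35% neighbours within 100 m and 45% beyond. PEP prevents a fraction e of cases in those dosed. Half of the arm 4 neighbour cases would have tested positive and been dosed. Arms are of equal size. The whole-village rule is not triggered.

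**Formula.** Share within 100 m = (household + neighbour cases remaining) / (those + cases beyond 100 m). The household term is multiplied by (1 - e) in arms 2, 3 and 4. The neighbour term is multiplied by (1 - e) in arm 3 and by (1 - e/2) in arm 4.

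**Result at e = 50%, post-enrolment cases only:**

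| Arm | Household | Neighbours | Beyond 100 m | Total | Share within 100 m |
|---|---|---|---|---|---|
| 1 | 0.20 | 0.35 | 0.45 | 1.0000 | 55.0% |
| 2 | 0.10 | 0.35 | 0.45 | 0.9000 | 50.0% |
| 3 | 0.10 | 0.175 | 0.45 | 0.7250 | 37.9% |
| 4 | 0.10 | 0.2625 | 0.45 | 0.8125 | 44.6% |
| Pooled | 0.50 | 1.1375 | 1.80 | 3.4375 | 47.6% |

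The pooled 100 m share is 1.6375/3.4375 = 47.6% against a true 55%. The pooled household share is 0.50/3.4375 = 14.5% against a true 20%. At e = 30% the pooled 100 m share is 1.8625/3.6625 = 50.9%, and at e = 60% it is 1.525/3.325 = 45.9%.

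**Adding enrolment-survey patients.** They predate PEP and keep the true share. If they are half of all patients, the 100 m share is (55 + 47.6)/2 = 51.3% at e = 50% and (55 + 45.9)/2 = 50.4% at e = 60%.

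**Whole-village rule.** Suppose every arm 3 village meets it. Cases beyond 100 m in arm 3 then also halve, to 0.225, and the arm 3 share returns to 0.275/0.50 = 55%. The pooled post-enrolment share becomes 1.6375/3.2125 = 51.0%.

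**Other true shares**, with half of the near cases in the household and post-enrolment cases only. A true 60% becomes 51.9% at e = 50% and 46.4% at e = 75%. A true 70% becomes 62.6% and 57.4%. If half of the cases expected without PEP are baseline cases, a true 60% becomes 56.3% and 54.2%.

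**Does the arm covariate in the distance model help?** Assume true rate ratios of 5 (household) and 2 (neighbours within 100 m) against 100 m or beyond, and the same spread of person-time over distance in every arm. At e = 50% the pooled rate ratios are

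- household: 5 × (1 + 0.5 + 0.5 + 0.5)/4 = 3.13
- neighbours: 2 × (1 + 1 + 0.5 + 0.75)/4 = 1.63

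A Poisson fit to the expected counts gives 3.13 and 1.63 both with and without the arm main effect. A main effect scales all distances in an arm alike, so it cannot represent an effect that differs by distance. In arm 1 alone the rate ratios stay at 5 and 2.

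**The case against.** Five counter-arguments have force.

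1. **Dilution by baseline patients.** The SAP includes them expressly. Madagascar enrols only at its second survey, so two surveys there precede trial PEP. A reader might infer from 47.6% that the plan will turn a true majority within 100 m into an apparent minority. The SAP does not support that: 47.6% leaves out the baseline patients, and with them at half of all patients the figure stays just above 50%. A reversal needs a true share only a little above 50%, together with high efficacy or few baseline patients.
2. **Whole-village rule.** Where it applies, PEP also removes distant cases and the distortion shrinks. The SAP does not say how often it will apply. It has no counterpart in arm 2.
3. **The overlay names no population.** The sentence on all patients belongs to the fingerprinting and K-function. Pooling in the overlay is inferred from the lack of any restriction, and the SAP sets no numerical rule for what counts as most.
4. **Village clustering.** A reader might extend the argument to the village proportions. Cases beyond 100 m can still belong to the same village, so no direction follows.
5. **Part of section 8.2 is apparently clean.** The 2019 distance model looks unaffected by trial PEP if the 2019 diagnoses are those of the first survey. The second model carries study arm, but as shown above that does not protect its distance gradient.

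These points limit the size and scope. None removes the selective loss of near cases among later patients in arms 2-4, and a later case linked to a baseline index patient in those arms still arises under PEP.

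**Conclusion.** The point holds for household clustering and the K-function, where pooling is explicit, and for the 100 m overlay, where it is inferred. To the extent that PEP works, the pooled household and 100 m shares are biased downwards. That direction follows from the allocation rule.

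The size cannot be known from the SAP. On the assumed values, the 100 m share falls from 55% to about 48% among post-enrolment cases, or to about 51% when enrolment-survey patients are half of the total. It falls less where whole villages are treated. The case for changing the plan is that a share read as the natural pattern would be understated, whether or not it crosses 50%.

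This is a secondary objective. The comparison of incidence between arms is not touched. The change is worth making before the clustering analysis is run.

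**What to change.** In SAP section 8.2:

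- Define molecular clusters once, on all patients, so that no link between a baseline patient and a later patient is cut. Forming clusters separately in subsets would itself lower apparent clustering.
- Report household clustering and the share of linked cases within 100 m by arm and by period (at or before the enrolment survey, and later). State the population of the overlay.
- Base the household and 100 m conclusions on cases found at or before the enrolment survey in all arms, including survey 1 on Madagascar, plus later cases in arm 1. Show later cases in arms 2, 3 and 4 by arm, as the pattern under PEP.
- In the 2019-to-2020 distance model, add an arm-by-distance term or report the arm 1 gradient.

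No new data are needed, only SAP wording, a split of planned tables and one model term. The cost is a wider interval for the headline share, because later patients of arms 2-4 no longer contribute to it.
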